### ***2.4. Descriptive Statistics***

Descriptive statistics for both eyes combined will be provided for endothelial cell density and adverse events. The statistics presented for continuous variables will include mean, median, standard deviation, number of eyes, minimum and maximum. The statistics for categorical variables will include sample size and percentage in the categories.

## **3. DATA SETS ANALYZED**

### ***3.1. Safety***

#### **3.1.1. EVALUABILITY STRATEGY**

All subjects enrolled in the study will be considered evaluable for the safety analysis. All data collected in the study will be considered evaluable for the safety analysis with one exception. For subjects who have their AcrySof® CACHET® L-series Phakic Lens explanted and not replaced with another AcrySof® CACHET® L-series Phakic Lens, the post-explantation endothelial cell density data will be excluded from the statistical analyses other than a post-explant endothelial cell loss analysis. The post-explantation data will be used in subject narratives. The final evaluability (exclusion of post-explantation endothelial cell density data) will be determined prior to database lock.

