
No

Masking:

None

Observer-Masked

Patient-Masked

Double-Masked

Randomization:

Yes

No

Group Assignment Ratio:

Concurrent Control:

None

No Treatment

Placebo

Active

Other

Specify:  
Specify:

Estimated Total Sample Size: Required: N/A

Planned: Up to 1321 eyes

Statistical Rationale Provided:  Yes See Section 11

No

Variable(s): Primary Efficacy

- None

Secondary Efficacy

- None

Primary Safety

- Central endothelial cell density
- Adverse events

Adverse Events:

[figure not shown]
Both volunteered and elicited

Other:

Analyses: The primary objective is to estimate the annualized endothelial cell loss rate (for up to 10 years following date of implantation) of subjects previously implanted with the ACRYSOF CACHET Phakic Lens (L-series) from clinical studies C-02-23, C-02-40, C-03-21 and C-05-57.

[figure not shown]
Combining data from this study with the data from the subjects' previous studies, the rate of endothelial cell density loss between consecutive visits will be calculated via a paired analysis and descriptive statistics on those rates will be presented. [REDACTED]

[REDACTED] Also, the percentage endothelial cell density decrease for each eye from baseline (6 month visit in previous study) to each visit will be calculated via a paired analysis and descriptive statistics for the actual and annualized loss rates will be presented.

The secondary objective is to collect additional safety data that may identify risk factors for eyes with significant endothelial cell loss.

Descriptive statistics will be provided for central [REDACTED] endothelial cell densities, [REDACTED]

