## **5. OBJECTIVE(S)**

The primary objective is to estimate the annualized endothelial cell loss (ECL) rate (for up to 10 years following date of implantation) of subjects previously implanted with the ACRYSOF CACHET Phakic Lens (L-series) within clinical studies C-02-23, C-02-40, C-03-21 and C-05-57.

The secondary objective is to collect additional safety data that may identify risk factors for eyes with significant ECL.

[figure not shown]

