### ***7.2. Inclusion Criteria***

1. Subjects previously implanted (including subjects who have had the lens explanted for any reason) with an ACRYSOF CACHET Phakic Lens (L-Series) from clinical studies C-02-23, C-02-40, C-03-21 and C-05-57 and are eligible for continued follow-up (ie, exited from their previous study).
2. Subjects are willing and able to complete the yearly postoperative study visits.
3. Subjects are able to understand and sign a statement of informed consent.

[figure not shown]

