## **8. STUDY DESIGN**

### ***8.1. Study Design***

Subjects enrolled in this study will attend postoperative visits for up to 10 years following the date of implantation and will be able to enroll at any time for the duration of this trial. These subjects will be followed postoperatively to Year 10/10A (3619 – 3740 days) at appropriate intervals as defined in Section 9.1.

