## **11. SAMPLE SIZE JUSTIFICATION**

[figure not shown]
The sample size will reflect the number of sites and subjects agreeing to participate.

All available and willing subjects meeting inclusion criteria will be included in the study (up to 778 subjects; up to 1321 eyes).

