**Analysis**

[figure not shown]
[figure not shown]
The primary objective is to estimate the annualized endothelial cell loss rate (for up to 10 years following date of implantation) of subjects previously implanted with the AcrySof® CACHET® Phakic Lens (L-Series) from clinical studies C-02-23, C-02-40, C-03-21 and C-05-57.

The secondary objective is to collect additional safety data that may identify risk factors for eyes with significant endothelial cell loss.

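### The objective concerns subjects implanted in four parent studies, but the visible analysis set is only those who later enrol, so self-selection can bias the annualized loss rate in an unknown direction

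*SAP*

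**What the plan says.** **Target.** Protocol section 5 asks for the annualized loss rate "of subjects previously implanted with the ACRYSOF CACHET Phakic Lens (L-series) within clinical studies C-02-23, C-02-40, C-03-21 and C-05-57". The Analysis paragraph of the SAP has the same aim: "The primary objective is to estimate the annualized endothelial cell loss rate (for up to 10 years following date of implantation) of subjects previously implanted".

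**Analysis set.** SAP 3.1.1 states: "All subjects enrolled in the study will be considered evaluable for the safety analysis". Protocol 10.1 agrees.

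**How subjects enter.** Protocol section 11 says: "The sample size will reflect the number of sites and subjects agreeing to participate". It adds: "All available and willing subjects meeting inclusion criteria will be included in the study (up to 778 subjects; up to 1321 eyes"). One inclusion criterion in Protocol 7.2 is: "Subjects are willing and able to complete the yearly postoperative study visits". Under Protocol 8.1 subjects "will be able to enroll at any time for the duration of this trial", and Protocol 9.1 lets the Entrance Visit fall at any visit from Year 4 to Year 10.

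**Use of parent-study data.** The Analyses entry of the protocol summary begins: "Combining data from this study with the data from the subjects' previous studies". Protocol 10.4.1.1 plans cell density tables that reach back to visits in the previous studies. SAP 4.1.2.2 computes percent change from the preoperative value at visits in both the previous studies and this one. It also counts eyes with onset of a loss of 30% or more, or a density of 1500 cells/mm² or less, from 6 months after implantation.

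**Safeguards.** All patients who meet the criteria are invited and explanted subjects stay in (Protocol 8.2 and 9.6). There are no exclusion criteria (Protocol 7.3).

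**The concern.** The population named in the objective and the population analysed are not the same. Whether a subject crosses from one to the other can depend on the outcome. A subject with a poor result may have left the clinic's care, or may be the one most eager to return. Explantation adds a route: Protocol 9.3.7 links its consideration to low cell density. An eye explanted during a parent study, whose subject does not enrol, then contributes nothing, not even its measurements before explantation.

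Two outputs are affected differently:

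- **Annualized rate to extension visits.** It may describe participants rather than implanted subjects. Confidence limits, which Protocol 10.4.1.1 lists among the statistics, would not reflect this.
- **Parent-visit tables and the threshold count.** An eye that lost 30% or more during a parent study, but whose subject or site did not enrol, is missing from both numerator and denominator, although its parent-study data already exist.

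**Working it through.** **Plan's own figure.** There is none to reproduce. The required sample size is given as N/A, and no precision, participation rate or loss rate is stated.

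**Inputs from the documents.** Ceilings of 778 subjects and 1321 eyes (Protocol 11). These imply 1321 − 778 = 543 bilateral and 778 − 543 = 235 unilateral subjects, or m = 1321/778 = 1.70 eyes per subject.

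**Assumed inputs.** Share enrolled p = 0.6 to 0.9. Absolute difference d in mean annualized loss, enrolled minus non-enrolled, 0.25 to 1.0 percentage points per year. Standard deviation (SD) of the eye-level rate 2 points per year, varied from 1 to 3. Within-subject correlation 0.5. The 1321 eyes are treated as the whole implanted cohort, which the documents do not state.

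**Step 1, bias.** The cohort mean is p × enrolled mean + (1 − p) × non-enrolled mean. Subtracting it from the enrolled mean gives

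bias = (1 − p) × (enrolled mean − non-enrolled mean), so |bias| = (1 − p) × d.

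**Step 2, yardstick.** The 95% half-width of the enrolled mean is 1.96 × SD × √[(1 + (m − 1) × 0.5) / (1321p)]. The design factor is 1 + 0.698 × 0.5 = 1.349. At p = 0.6 and SD 2 this is 1.96 × 2 × √(1.349/792.6) = 0.16.

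**Step 3, break-even.** Bias equals the half-width when d = half-width / (1 − p).

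| p | bias, d = 0.25 | bias, d = 0.5 | bias, d = 1.0 | half-width, SD 2 | break-even d |
|---|---|---|---|---|---|
| 0.6 | 0.10 | 0.20 | 0.40 | 0.16 | 0.40 |
| 0.8 | 0.05 | 0.10 | 0.20 | 0.14 | 0.70 |
| 0.9 | 0.025 | 0.05 | 0.10 | 0.13 | 1.32 |

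All entries are percentage points per year. For SD 1 to 3 the break-even d runs from 0.20 to 0.61 at p = 0.6, from 0.35 to 1.05 at p = 0.8, and from 0.66 to 1.98 at p = 0.9.

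**Step 4, which tables can be widened.** SAP 4.1.2.1 runs the annualized change from Month 6 to each scheduled visit in this study. A non-enrolled eye has no measurement at those visits, so its parent data cannot enter those rows. The parent-visit rows of Protocol 10.4.1.1, and the parent-study part of the threshold count in SAP 4.1.2.2, can take it.

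**The case against.** The strongest reply is that this is an openly voluntary extension, described as such, with no hypothesis test. The objective does not contain the word all. SAP 3.1.1 by itself only says that no enrolled subject is left out, which is not an error. Late entry is also partly structural: subjects must have exited their parent study, and point of entry follows the surgery date and the next available visit. Universal invitation and retention of explanted subjects reduce selection. Redacted passages in both analysis sections could hold an analysis of non-participants.

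Most of this stands, and it limits the point. The safeguards still do not reach subjects or sites that decline. The implanted cohort remains the natural reading of the objective, and the visible data-set definition is confined to enrolled subjects.

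A reader might go further in four ways that the documents do not support:

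- **That the rate is biased in a known direction, or by more than its sampling error.** Every input to the size is assumed. At 90% participation even a 1.0-point difference gives 0.10, below the 0.13 half-width. A 0.25-point difference stays below the half-width at all three participation rates in the table.
- **That adding non-enrolled eyes to the annualized rate would repair it.** They have no extension visits, and pooling their short follow-up with rates to Year 10 would blend different time windows.
- **That each extension visit should be reported over all implanted eyes still carrying the lens.** This needs lens status after parent-study exit for people who never enrolled, and the documents describe no such data.
- **That the plan has no analysis of non-participants.** Because of the redaction, only its absence from the visible text can be stated.

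**Conclusion.** The concern holds as a mismatch between the stated target and the visible analysis set. Self-selection can bias the annualized rate; direction and size cannot be found from the documents. Under the stated assumptions the absolute bias runs from 0.1 × 0.25 = 0.025 to 0.4 × 1.0 = 0.40 points per year. That is negligible at one end and larger than the assumed sampling error at the other.

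The part that can be put right concerns the parent-study period, where results would change if non-enrolled eyes differ. It is worth doing because it is cheap and shows readers how far participants resemble the implanted cohort up to parent exit. It does not remove selection after that point. It assumes that the parent-study databases are final when the analysis is run (the protocol's introduction describes two of the four studies as complete) and that the sponsor may use non-enrolled subjects' parent-study data.

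**What to change.** In the SAP:

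- **(a) Comparison.** Tabulate enrolled against non-enrolled L-series eyes, by parent study, with the enrolled share. Compare preoperative and Month 6 central cell density, last parent-study density, annualized loss from Month 6 to parent exit, and explant status at parent exit.
- **(b) Parent-study period.** Present the parent-visit density tables, the consecutive-visit loss tables, and the count of eyes with onset of a loss of 30% or more or a density of 1500 cells/mm² or less during the parent studies, for all implanted L-series eyes as well as for enrolled eyes.
- **(c) Extension period.** Keep the annualized rates from Month 6 to extension visits on enrolled eyes, label them so, and show number measured over number enrolled at each visit.

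If a redacted section already covers any of this, a cross-reference from SAP 3.1.1 is enough for that item.

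Cost: SAP wording, one data merge, and a second version of some tables. No new subjects or visits are needed. The downside is that parent-visit and extension-visit tables will rest on different populations, so each must be labelled.

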### ***8.2. Methods Used to Minimize Bias***

Randomization and masking are not used in this study. However, all investigators and study coordinators will receive common training (including specular image collection and angle measurements) to ensure consistent application of the methods specified in the protocol. Also, the same inclusion criteria are to be applied by all investigators and all patients meeting inclusion criteria will be invited to participate in the study. Furthermore, explanted subjects will not be discontinued. Bias will also be minimized by using a central reading center for corneal endothelial cell analysis. In addition, study duration will be sufficient to examine the effect of the lens on endothelial cells (ie, density [REDACTED]).

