#### **9.3.7. ENDOTHELIAL CELL DENSITY ANALYSIS**

Endothelial cell density [REDACTED] will be measured using the same methods as in the previous studies (C-02-23, C-02-40, C-03-21, C-05-57). The Konan Noncon-Robo specular microscope will be used to photograph corneal endothelial cells. Three images at the center of the cornea [REDACTED] shall be obtained.

Images shall be stored on the computer hard drive at the clinical site. Electronic copies of the images will be sent to a central reading center for analysis. For consistency, the central reading center ([REDACTED]) used for the previous studies, will be used for this study; Alcon personnel will not be involved in image analysis. The process for analyzing images at [REDACTED] will remain unaltered from that done in previous studies. Briefly, images received at [REDACTED] [REDACTED] will be reviewed by an initial reader and assessed for image quality. If image quality is acceptable then images will be analyzed. If images are deemed unanalyzable, then images will not be analyzed, and the site and Sponsor will be notified. (If there is a trend of unanalyzable images for a specific site/delegated study

personnel, retraining will be provided.) The subject will be asked to return and repeat the image capture and new images will be analyzed and used in the dataset. Analyzed images will be audited by a quality control reviewer [REDACTED]

Data reported by the central reading center will include endothelial cell density, [REDACTED]

[REDACTED] The site will receive a copy of the analysis to enter results in eCRFs.

The critical ECD threshold needed to sustain corneal endothelial cell function varies among individuals. Thus, it is critical to have regular examinations of the cornea every 6 months.

[figure not shown]
Criteria that may warrant more frequent examinations include:

- <1500 cells/mm^2 (central [REDACTED])
- >10% ECL in one year
- >30% ECL from preoperative baseline

[REDACTED]

When the central ECD approaches approximately 1500 cells/mm^2, the investigator should consider the potential need to undergo IOL explantation to reduce the risk of corneal decompensation and subsequent surgical interventions (such as corneal transplantation or DSEK). [REDACTED]

[REDACTED]

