### ***10.2. Analysis Data Sets***

#### **10.2.1. SAFETY**

All data collected in the study will be considered evaluable for the safety analysis with one exception. For subjects who have their ACRYSOF CACHET L-series Phakic Lens explanted and not replaced with another ACRYSOF CACHET L-series Phakic Lens, the post-explantation endothelial cell density data will be excluded from the statistical analyses. The post-explantation data will be used in subject narratives and graphs.

[figure not shown]

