#### **10.4.1. PRIMARY SAFETY**

##### **10.4.1.1. CENTRAL ENDOTHELIAL CELL DENSITY**

Descriptive statistics for central endothelial cell density, for each scheduled visit (including data from previous studies), will be provided. Descriptive statistics for central endothelial cell density chronic change (actual and percent) from baseline (6 month visit in previous study) to each scheduled visit will be provided. Descriptive statistics for central endothelial cell density change (actual and percent) between consecutive scheduled visits will be provided. All tables will be generated separately for first implanted eye, second implanted eye, and for both implanted eyes combined. Descriptive statistics include mean, median, standard deviation, sample size, minimum, maximum and confidence limits.

The mean rate of endothelial cell density decrease will be calculated via a paired analysis in order to calculate the mean of the differences between each reporting period.

[figure not shown]

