#### **3.1.2. HANDLING OF DROPOUTS OR MISSING DATA**

All data will be used in the analyses. No imputation will be carried out for missing data.

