##### 4.1.2.1. CHRONIC CHANGE FROM DAY 147-182 (MONTH 6 IN PREVIOUS STUDIES)

[figure not shown]
Descriptive statistics will be provided for each scheduled visit, for [REDACTED] central [REDACTED] endothelial cell density, for all eyes combined. The statistics presented for endothelial cell density (using the average from the analyzable images for each eye) will include mean, median, standard deviation, sample size, minimum, and maximum.

[figure not shown]
The percent change of mean endothelial cell density over time from Day 147-182 (Form 5 or 5A) in the previous studies to each visit in the current study will be calculated. The actual and annualized percent change of mean endothelial cell density from the Day 147-182 (Form 5 or 5A) exam to each scheduled visit in this study will be calculated and presented along with median, standard deviation, sample size, minimum and maximum. Tables presenting the mean, median, standard deviation, sample size, minimum and maximum of baseline (Form 5 or 5A in previous studies) endothelial cell density and cell density change from baseline to each scheduled visit in this study will be presented for all eyes combined.

[figure not shown]

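### In the visible SAP text, late-visit annualised loss is averaged only over eyes still carrying an L-series lens, so explants prompted by low cell density can make it too low

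*SAP*

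**What the plan says.** The primary objective is the annualised endothelial cell loss rate up to 10 years after implantation. The study population in both documents expressly includes subjects whose lens has been explanted.

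Four provisions decide which eyes enter the rate:

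- **Exclusion.** Protocol 10.2.1 states that for eyes explanted without an L-series replacement, "the post-explantation endothelial cell density data will be excluded from the statistical analyses". SAP 3.1.1 repeats this with one exception: "the post-explantation endothelial cell density data will be excluded from the statistical analyses other than a post-explant endothelial cell loss analysis". The visible text does not specify that exception further.
- **Missing data.** SAP 3.1.2: "No imputation will be carried out for missing data".
- **Summary.** SAP 4.1.2.1 presents "The actual and annualized percent change of mean endothelial cell density from the Day 147-182 (Form 5 or 5A) exam to each scheduled visit", for all eyes combined.
- **Link between outcome and removal.** Protocol 9.3.7 says that as central ECD nears about 1500 cells/mm², "the investigator should consider the potential need to undergo IOL explantation to reduce the risk of corneal decompensation".

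Protocol 8.2 lists among its measures against bias: "Furthermore, explanted subjects will not be discontinued". The protocol also plans consecutive-visit rates. Its Summary says "the rate of endothelial cell density loss between consecutive visits will be calculated via a paired analysis", and Protocol 10.4.1.1 adds "Descriptive statistics include mean, median, standard deviation, sample size, minimum, maximum and confidence limits".

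**The concern.** An eye leaves the visit means when its lens is removed, and one stated prompt for considering removal is a low value of the variable being averaged. Eyes that lose cells fastest are then more likely to be absent from the later means. Keeping explanted subjects in follow-up does not protect this rate, because their later ECD is not used in it.

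No hypothesis test is planned (Protocol 10.7), so the descriptive rate is the main result. An error from this source would run in one direction, towards a more favourable rate for the lens. It would fall on the late visits, which are what this extension adds to the earlier studies.

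**Working it through.** **Inputs from the documents.** The 1500 cells/mm² level (Protocol 9.3.7), up to 1321 eyes (Protocol 11), the Month 6 baseline (SAP 4.1.2), and visits to Year 10, half-yearly after Year 5 (Protocol 17). The documents state no loss rate, SD or explant count, so there is no planned figure to reproduce. Every other input below is an assumption. I read the annualised change as a within-eye quantity, as the Protocol Summary describes it.

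**Step 1: identity.** Let f be the share of eyes removed before a visit. Then

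mean over all eyes = (1 − f) × on-lens mean + f × removed-eye mean,

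so gap = all-eye mean − on-lens mean = f × (removed-eye mean − on-lens mean).

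This needs no distributional assumption. The gap is zero if removed eyes lose at the same rate as the others, as may hold for explants unrelated to ECD.

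**Step 2: annualised loss of an eye that falls to 1500.** Assume a Month 6 ECD of 2700. The loss is (2700 − 1500)/2700 = 44.4%.

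- Reached at Year 10: 44.4/9.5 = 4.7% per year.
- Reached at Year 7: 44.4/6.5 = 6.8% per year.
- Over Month 6 values of 2400 to 3000, the range is 37.5/9.5 = 3.9 to 50/6.5 = 7.7% per year.

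**Step 3: effect on the mean.** Assume an on-lens mean of 1.5% per year and all 1321 eyes counted.

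| Eyes removed | f | Gap if removed eyes lose 4.7%/yr | Gap if they lose 6.8%/yr |
|---|---|---|---|
| 13 | 1% | 0.03 | 0.05 |
| 66 | 5% | 0.16 | 0.27 |
| 132 | 10% | 0.32 | 0.53 |

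**Step 4: simulation.** There were 60 scenarios of 300,000 eyes. Assumptions:

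- Month 6 ECD 2700 (SD 300) and measurement CV 3%.
- Eye-level loss normal or gamma, linear or log-linear.
- Mean/SD 1/1, 1.5/1, 2/1, 1.5/1.5 or 2/2% per year.
- Explant probability 0.1, 0.5 or 0.9 at each visit with observed ECD at or below 1500.

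The comparator is the same eyes with none removed.

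| | Normal rates | Gamma rates |
|---|---|---|
| Year 10 gap, range (points/yr) | 0.00–0.33 | 0.00–0.46 |
| Year 10 gap, median | 0.01 | 0.04 |
| Scenarios at about 0.10 or more | 4 of 30 | 7 of 30 |
| Largest gap with SD 1 | 0.03 | 0.06 |
| Linear, 1.5/1.5, probability 0.5 | 0.06 | 0.18 |

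At Year 5 the gap is at most 0.03 in all 60. The starting density matters. With equal mean and SD and probability 0.5, the largest gap (normal/gamma) is 0.49/0.56 if Month 6 ECD is 2400, and 0.16/0.32 if it is 3000.

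**Step 5: does a last on-lens rate repair it?** In the same 60 scenarios, letting each removed eye contribute its annualised loss to its last on-lens reading came within 0.02 (normal) and 0.04 (gamma) of the comparator, always towards more loss. Carrying the ECD value forward instead left the rate up to 0.17 too low. Each simulated eye has a constant rate, which favours the first method.

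Dropout matters here. With 50% random dropout over Years 5–10 (linear, probability 0.5), carrying removed eyes' rates to every later visit regardless of attendance overstated the rate by about 0.09 (gamma 1.5/1.5), 0.11 (normal 2/2) and 0.25 (gamma 2/2). Restricting it to subjects still in the study cut this to 0.02 or less.

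**The case against.** **Redaction.** The SAP contents list a blacked-out heading at page 11 between section 4.1.2 (page 10) and section 4.2 (page 15), and the Protocol Summary is blacked out directly after the consecutive-visit sentence. A longitudinal model or sensitivity analysis could be there. This stands. A reader might infer that no analysis including explanted eyes is planned, but the documents do not support that.

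**Visible safeguards.** Post-explant data go to narratives and graphs (Protocol 10.2.1; narratives also in SAP 3.1.1). Each removal during the study needs a Serious Adverse Event Form (Protocol 8.1.1) and is listed by eye and onset day (SAP 4.2.2). SAP 4.1.2.2 counts eyes with at least 30% loss or ECD at or below 1500. So the number and timing of removals are largely recoverable. This also stands, but none of these items gives a rate that includes explanted eyes. The protocol's consecutive-visit changes reduce the problem without removing it. In the simulation, rates pooled over visits were still too low by at most 0.02 (log-linear) and 0.13 (linear) with normal rates, and by 0.08 and 0.36 with gamma rates.

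**Target.** The comparator, in which no lens is removed, is a hypothetical that neither document adopts. Excluding post-explant ECD is reasonable, since those readings mix lens effect, removal surgery and the course without the lens. A reader might infer that the exclusion is an error. It is not, and simply adding those readings back would not answer the question.

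**Size.** Protocol 9.3.7 asks only for consideration of explantation, and cataract is the example of removal given in Protocol 8.1.1. For scale, with an assumed 500 eyes at Year 10 and SD 1–2, the 95% half-width is 1.96 × SD/√500 = 0.09–0.18 before clustering. That is wider than the typical simulated gap. This supports a minor grading.

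**Conclusion.** The point holds as a possibility confined to the visible tables. If some removals follow low ECD, the late-visit means understate on-lens loss. The direction follows from the exclusion, the absence of imputation and the ECD-linked prompt, taken together.

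The size is unknown. Under assumed inputs it runs from negligible to about 0.4–0.5 points per year at Year 10, slightly more if Month 6 density is low. It is usually below 0.1 and about zero at Year 5. The larger values need widely spread loss rates and frequent ECD-driven removal.

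A reader might go further and conclude that the 10-year rate will be materially biased. The documents do not support that, because they give no explant count and no loss rates, and low ECD is only one possible reason for removal. Severity: minor.

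**What to change.** In SAP 4.1.2, keep the exclusion and every planned table, and add two items:

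1. **Explant table.** Beside each visit mean, give the number of eyes explanted before that visit, by reason, with their annualised loss from Month 6 to the last on-lens reading. With the identity in Step 1, a reader can then gauge the gap.
2. **One sensitivity analysis.** At each visit after explantation, an explanted eye contributes its last on-lens annualised rate (the rate, not the ECD value) only if the subject is still in the study and attended that visit. Explanted and on-lens eyes are then subject to the same dropout. Eyes with no on-lens reading after Month 6 are counted but not included. Report a 95% confidence interval clustered by subject, because the eye is the unit of analysis (SAP 2.3) and many subjects contribute two.

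Labelling the visit tables as covering eyes with an L-series lens in place is optional. If the redacted text already holds an equivalent analysis, cite it beside the visit tables instead.

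The cost is SAP wording and a little programming, with no new data. The downsides are that the analysis assumes loss before explantation would have continued at the same rate, it errs slightly towards more loss, and the reported rate may look less favourable.
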